1.0 Rationale and Specific Aims

While the barriers to community reintegration after traumatic brain injury (TBI) are multifactorial, memory and learning deficits are the most frequent targets for intervention in patients with TBI. The ability to (re)learn information is critical to a person's potential to benefit from therapy, to follow medical recommendations, to maintain positive social relationships, and to be successful at school or work. Yet, the last several decades have seen limited progress in developing restorative therapies for memory and learning deficits in this population.

In the cognitive neuroscience literature, evidence has accumulated that people with and without brain damage learn more when the context of learning is varied across time and space. Yet, rehabilitation typically occurs in a constrained context (i.e., the same therapy room at the same time of day). In memory rehabilitation, each opportunity to retrieve information strengthens that information in the neocortex, and is thus both an opportunity for assessment and intervention. Increasing the contextual variance of learning opportunities (i.e., in the daily lives and contexts of patients) may improve the rehabilitation potential of patients with TBI, in addition to increasing the potential for interventions that extend beyond an acute timeframe for service delivery.

There is critical need for technologies that move beyond the constrained therapy context to deliver interventions across time and space. In the proposed study, we focus on developing a technology-delivered system that extends the timing and context of memory exposures beyond current service delivery models. We aim to refine the technology for future use in research assessment and intervention contexts, with the long-term goal of improving memory care for individuals with TBI in their daily lives and across the lifespan. After taking into account feedback from real users, this system may also eventually be extended to other areas of TBI management and has the potential to improve both short-term and chronic care for the millions of Americans currently living with brain injury-related disability.

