4.0 Study Procedures

The technology being tested involves receiving intermittent text messages over the course of a week with links to respond to memory prompts on the Gorilla mobile behavioral experiment webpage.

Pilot and Feasibility of MEMI for Chronic Traumatic Brain Injury
NCT06375421

This pilot will include 40 participants: 20 with a history of chronic moderate-severe TBI and 20 demographically-matched non-injured peers. Participation in the study will last two weeks for each person, with one week in each of two conditions:

- **Blocked (Active Comparator) Condition:** Participants complete their initial learning session on the target words, then immediately receive all of the exposures to each of the items in a single block. They do not complete any more retrieval sessions until one week later, when they complete a 15-minute test for their memory of all of the trained items.
- **MEMI Spaced Retrieval (Intervention) Condition:** Participants complete their initial learning session, and the subsequent retrieval sessions are spaced out over the course of the week (two short retrieval sessions each day) using MEMI. Then, they complete a 15-minute test for their memory of all of the trained items at the end of the week.

Outcome measures include:

- **Acceptability (Primary): Acceptability of Intervention Measure:** At the end of each week, participants complete this four-item measure regarding the acceptability of each intervention condition. Scores range from 4 to 20, with higher scores indicating higher acceptability.
- **Feasibility (Primary): Session Engagement:** In each condition, we measure the number of possible sessions that each participant completes. In the Blocked condition, the total number of possible sessions is two. In the MEMI condition, the number of possible sessions is 12. Higher number of sessions completed indicates better engagement and higher feasibility.
- **Efficacy (Secondary/Preliminary): Memory at 1 week:** At the end of each week, participants complete memory tasks to assess their memory for the trained information. Measures include:
 - *Free recall of word forms:* The number of target word forms that participants can free type without cueing (0=did not remember any words- worse to 16=remembered all the words - better)

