 - *Cued recall of word forms:* The number of target word forms that participants remember in response to prompting (i.e., typing the word that labels a given image) (0=did not remember any words- worse to 16=remembered all the words - better)
 - *Cued recall of word meanings:* The number of target word meanings that participants remember in response to prompting (i.e., typing the definition for a given word) (0=did not remember any words- worse to 16=remembered all the words - better)
- **Other: Number of Spatial Contexts:** At the beginning of each retrieval session, we ask participants to give their spatial context (the physical location in which they are completing the session, e.g., home or work). We report the number of different spatial contexts in which participants

completed sessions in each condition. A higher number of spatial contexts indicates more variance in the contexts of retrieval opportunities, which is a goal of this technology.

5.0 Reporting of Adverse Events or Unanticipated Problems involving Risk to Participants or Others

Although serious adverse events are unanticipated given the nature of this study, the PI will evaluate all participant concerns for severity, relationship to the research, and actions to be taken, and immediately report any serious adverse events or unanticipated problems involving risks to participants to the IRB.

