7.0 Statistical Considerations

This phase of the study is descriptive and is designed to inform the research team regarding which aspects of using MEMI are challenging, or represents a barrier to use, for individuals with TBI. We collect preliminary pilot data on acceptability, feasibility, and the effects of technology-delivered spaced retrieval on memory in TBI. These findings will be used to refine the technology for future research and clinical trials.

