**NCT06375421 – Statistical analysis plan**

For this pilot study, we calculated descriptive statistics for participant characteristics, engagement (number of sessions completed), acceptability (Acceptability of Intervention Measure), and preliminary efficacy using R. Baseline participant characteristics were calculated for each group (TBI and non-injured comparison groups). Engagement, acceptability, and preliminary efficacy analyses were conducted within each group between the two conditions (Intervention: MEMI and Active Comparator: Blocked). For preliminary efficacy, we used paired-samples t-tests within each group to compare free recall at the 1-week assessment between the two conditions. We also conducted supplementary analyses assessing cued word form recall and cued definition recall at the 1-week assessment. Analyses were conducted using a complete-case approach.

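### Number of spatial contexts: the count shows how many places were reached, not how MEMI sessions were spread over them; a MEMI-only share of sessions outside the most-used place would show this

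*Protocol*

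**What the plan says.** Protocol section 4.0 lists the number of spatial contexts under the label Other. On data collection it says: "At the beginning of each retrieval session, we ask participants to give their spatial context". On reporting, the sentence starting "We report the number of different spatial contexts in which participants" goes on to say that the number is given for each condition. The interpretation follows: "A higher number of spatial contexts indicates more variance in the contexts of retrieval opportunities, which is a goal of this technology".

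The same section sets the session totals under the engagement outcome: "In the Blocked condition, the total number of possible sessions is two" and "In the MEMI condition, the number of possible sessions is 12".

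Section 1.0 explains why place matters. It says that "rehabilitation typically occurs in a constrained context (i.e., the same therapy room at the same time of day", and presents MEMI as a way to move beyond that. Section 7.0 calls this phase descriptive and adds: "These findings will be used to refine the technology for future research and clinical trials".

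Apart from participant characteristics, the SAP's list of descriptive statistics covers "engagement (number of sessions completed), acceptability (Acceptability of Intervention Measure), and preliminary efficacy using R". Spatial context is not mentioned.

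**The concern.** The protocol treats a larger count as more variance in the contexts of retrieval. How many places were used and how sessions were divided among them are different features of the data, and the count carries only the first. A participant who does eleven sessions at home and one at work has the same score as one who divides the week equally between the two.

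What is at stake is how well the pilot answers a question that it sets itself. A count of 1 is clear: everything happened in one place. A count of 2 or 3 leaves open whether MEMI was really used across settings or nearly always in one setting with an occasional exception. Those two patterns could point the developers in different directions when they refine the technology, and the planned summary cannot tell them apart. Because the SAP omits the outcome, it does not fill the gap.

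**Working it through.** The documents give no figure to reproduce here: no location data, target or threshold. The main check is enumeration and needs no assumption about people's habits.

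**Inputs.** Possible MEMI sessions: n = 12 (Protocol 4.0, engagement outcome). Location is asked at each retrieval session (Protocol 4.0). Number of different places: k.

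**Formula.** Let the share be the proportion of sessions outside the most-used place.
- Smallest share for a given k: every other place is used once, so (k − 1)/n.
- Largest share: sessions as even as possible, so 1 − ceil(n/k)/n.

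**Results for n = 12.**

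| Count k | Smallest share | Largest share |
|---|---|---|
| 1 | 0/12 = 0% | 0/12 = 0% |
| 2 | 1/12 = 8.3% (11+1) | 6/12 = 50% (6+6) |
| 3 | 2/12 = 16.7% (10+1+1) | 8/12 = 66.7% (4+4+4) |
| 4 | 3/12 = 25% | 9/12 = 75% |

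**Does a higher count mean more variance?** Compare 10+1+1 with 6+6. The counts are 3 and 2; the shares are 16.7% and 50%. The Simpson index, 1 − Σp², agrees: 1 − (100 + 1 + 1)/144 = 0.292 against 1 − (36 + 36)/144 = 0.500. The protocol's interpretation would rank these two participants the wrong way round on spread. Within a count of 2, the index runs from 1 − (121 + 1)/144 = 0.153 for 11+1 to 0.500 for 6+6.

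**Sensitivity to the denominator.** The protocol does not say which sessions make up the 12. Five days of two sessions plus learning and test gives 5 × 2 + 2 = 12; six days of two retrieval sessions also gives 6 × 2 = 12. If only 10 sessions carry a location, a count of 2 covers 1/10 = 10% to 5/10 = 50%, and a count of 3 covers 2/10 = 20% to 6/10 = 60%. The conclusion does not change.

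**Illustration with assumed habits.** Suppose a participant has two places and does each of 12 independent sessions in the second with probability q. The documents give no value for q, so a range is shown. The expected count is 2 − (1 − q)¹² − q¹². The expected share is the binomial mean of min(x, 12 − x)/12.

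| q | Expected count | Expected share |
|---|---|---|
| 0.1 | 1.72 | 10% |
| 0.2 | 1.93 | 20% |
| 0.3 | 1.99 | 29% |
| 0.5 | 2.00 | 39% |

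From q = 0.2 to 0.5 the count hardly moves, while the share roughly doubles. This shows how the loss of information could look in group averages; the main result does not depend on it.

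**The case against.** The outcome is named as a number, labelled Other, and has no test, threshold or decision attached. Number of places and evenness of use are both ordinary senses of variance, and no passage makes evenness a goal. Section 1.0 opposes one constrained setting to varied settings, and a count of 1 against more than 1 speaks directly to that. Section 7.0 names acceptability, feasibility and memory effects as the pilot data, not spatial spread. The share is also one choice among several: 6+6 and 6+2+2+2 both give 50%, it is coarse when few sessions are completed, and it inherits the lack of any rule for what counts as a different place.

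Much of this stands. It is why the point is minor, why the count should stay, and why a plain table of sessions by place would do as well. It does not rescue the general statement that a higher count indicates more variance, since on any measure of spread 10+1+1 is less varied than 6+6.

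A reader might infer more than the documents support. One inference is that comparing the counts between conditions is misleading, because MEMI offers 12 sessions and Blocked two. Section 4.0 states both totals just before this outcome, and reaching more places through more sessions is what MEMI is designed to do. The size of any difference cannot be worked out, because it depends on habits about which the documents say nothing. Another inference is that location might be asked at only one Blocked session. The wording does not settle this, but section 4.0 reads more naturally as treating both the block and the one-week test as retrieval sessions. A third is that the SAP's silence means that the count will go unreported; the protocol itself commits to reporting it.

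**Conclusion.** The point holds in a limited form. The count is a valid description of how many places were reached, but the protocol's interpretation of it as variance in context is not true in general. With 12 sessions, a count of 2 leaves the share outside the main place anywhere from 8% to 50%, and a count of 3 anywhere from 17% to 67%. These ranges rest only on the stated 12 sessions, each with a recorded place; with 10 recorded locations they become 10% to 50% and 20% to 60%.

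The consequence is small. This is an optional improvement to a descriptive outcome in a pilot. It should not be taken to mean that the outcome is invalid or that any primary or efficacy result is in doubt: acceptability, engagement and recall do not use it.

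**What to change.** In Protocol section 4.0 and in the SAP:

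1. Keep the count, and describe it as the number of different places reached rather than as variance in context.
2. Add, for MEMI only, each participant's share of completed sessions outside the most-used place. The denominator is the number of sessions with a recorded location, reported beside the share. Summarise by group with median and range. A table of sessions by place for each participant would serve equally, since the share can be read from it. The restriction to MEMI is because two Blocked sessions allow only 0% or 50%.
3. List the outcome in the SAP. The SAP is written in the past tense; if the analysis is already done, report the share labelled as added later.

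The cost is one more descriptive statistic from locations already asked for, and a more modest reading of the count. The share is coarse when few sessions are completed: with 6 sessions, a count of 2 cannot give less than 1/6 = 17%. It complements the count and should not replace it.

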6.0 Study Withdrawal/Discontinuation

Participants are free to withdraw from the study at any time by contacting the PI. There is no penalty for early withdraw, and participants will receive payment proportional to the amount of the study completed. This is made clear during the informed consent process.

7.0 Statistical Considerations

This phase of the study is descriptive and is designed to inform the research team regarding which aspects of using MEMI are challenging, or represents a barrier to use, for individuals with TBI. We collect preliminary pilot data on acceptability, feasibility, and the effects of technology-delivered spaced retrieval on memory in TBI. These findings will be used to refine the technology for future research and clinical trials.

8.0 Privacy/Confidentiality Issues

Only KSP approved by the IRB will have access to research information. Participant survey data will be entered and stored electronically in REDCap. KSP will assign participants a unique subject ID associated with their identifiable information in REDCap. Original paper copies of any surveys will be de-identified and filed in a locked file cabinet. Participant contact information will be password protected and stored separately from research data, without any health information, on a secure VUMC server. Participant information collected for payment purposes will be stored separate from research data in a locked file cabinet.

In order to minimize the risks of loss of privacy, all research-related conversations with participants will take place in private testing rooms on a private web conference session or phone call when data are collected remotely. Recordings from participant interviews will be saved with the unique subject ID

Pilot and Feasibility of MEMI for Chronic Traumatic Brain Injury

NCT06375421

on a secure VUMC server. Twilio, the platform that delivers the mobile phone intervention, is integrated into REDCap in order to initiate and tailor the intervention (e.g., name, cell phone number, preferred time of day to receive text messages). Twilio will be used to send text messages at pre-designated times. Each of these messages contains a link to the secure web platform where participants will complete the memory task. Individual participant responses to the memory task are only accessible by KSP through a secure password protected portal.

**NCT06375421 – Statistical analysis plan**

For this pilot study, we calculated descriptive statistics for participant characteristics, engagement (number of sessions completed), acceptability (Acceptability of Intervention Measure), and preliminary efficacy using R. Baseline participant characteristics were calculated for each group (TBI and non-injured comparison groups). Engagement, acceptability, and preliminary efficacy analyses were conducted within each group between the two conditions (Intervention: MEMI and Active Comparator: Blocked). For preliminary efficacy, we used paired-samples t-tests within each group to compare free recall at the 1-week assessment between the two conditions. We also conducted supplementary analyses assessing cued word form recall and cued definition recall at the 1-week assessment. Analyses were conducted using a complete-case approach.

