3.0 Enrollment/Randomization

No randomization will occur. The order of condition/word list combination will be pre-determined, and participants will be assigned to the next available combination based on when they join the study (i.e., a counterbalanced within-person crossover design).

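### The SAP's paired t-tests omit condition order and word list, the two factors the design counterbalances

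*SAP*

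**What the plan says.** Protocol section 3.0 describes "a counterbalanced within-person crossover design" without randomization. The allocation rule is: "The order of condition/word list combination will be pre-determined, and participants will be assigned to the next available combination", in order of joining. It does not state how many combinations or lists there are, or whether the TBI and non-injured groups are counterbalanced separately.

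Section 4.0 plans 20 participants per group, with one week in each condition. Free recall is scored from 0 to 16.

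The SAP analyses each group separately: "we used paired-samples t-tests within each group to compare free recall at the 1-week assessment between the two conditions". It adds: "Analyses were conducted using a complete-case approach". Neither document mentions a week, order or list term, a check for such effects, or a table of participants per combination.

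**The concern.** Counterbalancing treats week and list as nuisance factors worth controlling. Each person's MEMI-minus-Blocked difference contains any change between week 1 and week 2, with a sign set by the order, and any difference in list difficulty, with a sign set by the list allocation. A paired t-test on these differences treats that known structure as random error.

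Two consequences follow:

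- **Even splits within a group.** The contributions cancel in the mean but inflate its standard error, so the test is conservative and the interval too wide.
- **Uneven splits within a group.** The contributions do not fully cancel, and part of the week or list effect is reported as a MEMI effect.

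Uneven splits could arise from complete-case losses, since Protocol section 6.0 allows withdrawal at any time. They could also arise if one allocation list served both groups. Without counts a reader cannot tell which situation applies. Section 7.0 says of the results: "These findings will be used to refine the technology for future research and clinical trials". The precision and any bias of this estimate would therefore carry forward.

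**Working it through.** The plan gives no power, SD or effect size, so there is no figure to reproduce.

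**Inputs from the documents.** Up to 20 pairs per within-group test and two one-week periods (Protocol 4.0); counterbalanced order and list (Protocol 3.0); paired t-test on complete cases (SAP).

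**Assumptions.** Two orders by two list allocations; two-sided 5% level; residual SD of the difference σ = 3 words, varied from 2 to 4; additive week effect π and list effect λ of 0 to 1.5 words; no carry-over.

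**Model.** D = τ + sπ + lλ + e, where s = ±1 is order, l = ±1 is list allocation, SD(e) = σ, and τ is the MEMI effect.

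**1. Bias of the paired t-test.** The mean of D has expectation τ + π·mean(s) + λ·mean(l). For one factor split n1:n2, the fraction carried into the estimate is (n1 − n2)/n. Cells are listed as order 1/list A, order 1/list B, order 2/list A, order 2/list B.

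- 6/4/4/6: both margins 10:10, bias 0. Unequal cells alone do no harm.
- 6/6/4/4: order 12:8, lists 10:10, bias (12 − 8)/20 × π = 0.2π, or 0.2 word for a 1-word week effect.
- 7/5/5/3: both margins 12:8, bias 0.2π + 0.2λ, or 0.4 word at 1 word each with the same sign.

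**2. Precision with even margins, n = 20.**

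- Unadjusted half-width: 2.0930 × √[(σ² + (π² + λ²) × 20/19)/20], on 19 df.
- Half-width with order and list terms: 2.1098 × σ/√20, on 17 df.
- At σ = 3 and π = λ = 1: 2.0930 × √(11.105/20) = 1.56, against 2.1098 × 3/4.472 = 1.42. The ratio is 1.10.

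| π = λ (words), σ = 3 | 0 | 0.25 | 0.5 | 0.75 | 1 | 1.5 |
|---|---|---|---|---|---|---|
| Unadjusted/adjusted width | 0.992 | 0.999 | 1.021 | 1.055 | 1.102 | 1.226 |

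The widths are equal at π = λ = 0.087σ, about 0.26 word. At 1 word each the ratio is 1.226 if σ = 2 and 1.055 if σ = 4.

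**3. Type I error of the paired t-test** (100,000 simulations per scenario, σ = 3, effects of the same sign).

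| Cells | π = λ = 0.5 | 1 | 1.5 |
|---|---|---|---|
| 5/5/5/5 | 4.4% | 3.2% | 1.7% |
| 6/6/4/4 | 4.6% | 3.9% | 2.7% |
| 7/5/5/3 | 5.2% | 6.1% | 6.6% |

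The adjusted model stays between 4.8% and 5.2% throughout.

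**4. Cost of adjusting when both effects are zero.** Even margins: 2.1098/2.0930 = 1.008. Order 12:8: 1.008 × 1/√(1 − 0.04) = 1.029. Both margins 12:8: 1.008 × √(20/18.4) = 1.051.

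**5. Separate check in SD units.** With even margins and effects of 0.5 SD each (1.5 words at σ = 3), the average standard error rises from 0.220 to 0.273 SD. For a true effect of 0.66 SD, power falls from about 80% to 64%. Three losses from one cell (5/5/5/2, n = 17) bias the paired estimate by (3/17) × 0.5 + (3/17) × 0.5 = 0.18 SD; the adjusted estimate is unbiased.

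**The case against.** The best defence is that the design already does the work. Twenty per group divides evenly over four combinations, and with even margins the paired t-test is unbiased and conservative. No passage shows uneven margins or gives a loss rate, and mild losses do little. At 1 word each with the same sign, one person lost from one cell (5/5/5/4) gives a bias of 0.11 word and type I error of 3.4%; two lost (5/5/5/3) give 0.22 word and 4.1%.

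The 6.1% figure needs both margins at 12:8 and both effects at 1 word with the same sign. With opposite signs the bias is zero and type I error is 3.1%; with only one effect present it is 4.8%. The precision loss also depends on assumed effects. With a single 1-word effect and even margins, the unadjusted interval is only 4.8% wider (half-width 1.48 against 1.42). Below the break-even, adjustment slightly loses. Efficacy is secondary in a descriptive pilot, and the SAP is written in the past tense, so a new model may be post hoc.

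All of this stands as a limit on importance, and false-positive inflation is not the main issue. It does not remove the gap: the documents confirm neither the number of combinations nor balance within each group, and the SAP plans no counts that would show it. A further objection, that ±1 list coding presumes two list allocations, is met by entering list as a factor if there are more.

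**Conclusion.** The concern holds, with moderate importance. The SAP's only named inferential test ignores the factors that the protocol counterbalances. With even margins the consequence is lost precision: at an assumed SD of 3 words, 2% wider intervals when both effects are 0.5 word, 10% at 1 word and 23% at 1.5 words. With uneven margins the estimate is also biased, by 0.2 word for a 12:8 order split and a 1-word week effect, and by up to 0.4 word if both margins are 12:8 and both effects are 1 word.

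All sizes rest on the assumed two-by-two layout, SD and effects, none of which the documents supply. Whether bias is possible depends on counts that the plan does not ask for.

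**What to change.** Suggested SAP wording:

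> Within each group, each complete participant's MEMI-minus-Blocked difference in free recall is regressed on condition order and word-list assignment, each coded +1/−1. The intercept is the MEMI effect and is reported with its 95% CI. Numbers of complete participants per order-by-list combination are tabulated by group. If order or list is constant, or the two are collinear, in a group, only the estimable terms are included and this is stated.

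If there are more than two list allocations, enter list as a factor with sum-to-zero coding, so that the intercept keeps its meaning. If the t-test results already exist, report them alongside and label the adjusted estimate as added later. Separate counterbalancing lists per group help only if enrolment is still open; otherwise they are for the next study.

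The cost is one linear model per group in R, one count table and two degrees of freedom (critical t 2.110 instead of 2.093), with no new data. The price in interval width if both effects are nil is worked out in step 4. The change does not address carry-over.

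### The SAP's complete-case sentence does not exempt session engagement; if a case must be complete across both weeks, early stoppers are deleted and this primary count can be overstated

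*SAP*

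**What the plan says.** The SAP is one paragraph. It states that "Engagement, acceptability, and preliminary efficacy analyses were conducted within each group between the two conditions", describes paired t-tests on free recall and supplementary analyses of the two cued-recall measures, and closes with "Analyses were conducted using a complete-case approach". It does not say what makes a case complete or limit the sentence to particular outcomes.

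Protocol section 4.0 makes session engagement a primary outcome: "In each condition, we measure the number of possible sessions that each participant completes". The maximum is 2 in Blocked and 12 in MEMI, and a higher count is read as higher feasibility. Acceptability, also primary, is collected once per condition: "At the end of each week, participants complete this four-item measure regarding the acceptability of each intervention condition".

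Section 3.0 describes "a counterbalanced within-person crossover design", and section 4.0 adds: "Participation in the study will last two weeks for each person, with one week in each of two conditions". Section 6.0 allows withdrawal at any time and says that "participants will receive payment proportional to the amount of the study completed". Neither document says how a participant who stops early enters the engagement count.

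**The concern.** A complete-case rule has an obvious meaning for a paired recall t-test: a pair needs both 1-week tests. Engagement is different in kind. Someone who starts MEMI and stops after 3 of 12 sessions has an observed engagement of 3. Deleting that person removes a low value that the measure exists to record.

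In a two-week crossover analysed between conditions within each group, a complete case can readily be taken to mean that both weeks are present. On that reading the engagement figure describes only people who finished. Section 7.0 of the protocol says this phase should show "which aspects of using MEMI are challenging, or represents a barrier to use, for individuals with TBI", and people who stop during the MEMI week carry part of that information. No feasibility threshold is stated, so no formal decision would change. What is at stake is whom the reported primary figure describes.

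**Working it through.** The documents state no engagement result, target or dropout rate, so there is no planned figure to reproduce. The calculation below is illustrative.

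**Inputs from the protocol (section 4.0):** n = 20 per group; maximum 12 sessions in MEMI and 2 in Blocked.

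**Assumptions:** k participants stop in the MEMI week after an average of s sessions, and completers average c. Base values are c = 11 and s = 3 (range 1 to 6), with k = 2 or 4.

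**Formulas (everyone starts MEMI):**
- Mean over all starters = ((n − k)c + ks)/n
- Mean after deleting stoppers = c
- Overstatement = (k/n)(c − s), which is positive only if s < c

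**MEMI week, c = 11.** After deletion the figure is always 11/12 = 91.7%.

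| k | s | All starters | Overstatement (points) |
|---|---|---|---|
| 2 | 3 | (18×11 + 2×3)/240 = 204/240 = 85.0% | 6.7 |
| 4 | 3 | (16×11 + 4×3)/240 = 188/240 = 78.3% | 13.3 |
| 4 | 1 | (16×11 + 4×1)/240 = 180/240 = 75.0% | 16.7 |
| 4 | 6 | (16×11 + 4×6)/240 = 200/240 = 83.3% | 8.3 |

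In sessions, the base cases are 10.2 against 11.0 (k = 2) and 9.4 against 11.0 (k = 4).

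**The week of stopping matters.** Suppose four people stop, two in MEMI (s = 3) and two in Blocked.
- Blocked second: the two Blocked stoppers already have MEMI counts. If these equal the completers' 11, the all-starter figure is 204/240 = 85.0%, a gap of 6.7 points.
- Blocked first: those two never start MEMI, so there are 18 starters, and (16×11 + 2×3)/(18×12) = 182/216 = 84.3%, a gap of 7.4 points.
- If instead all four stop in Blocked, the MEMI gap is zero, again provided that those who had already done MEMI match completers.

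**Blocked condition.** If stoppers complete 1 of 2 sessions and completers 2, the all-starter mean is (18×2 + 2×1)/20 = 1.90 for two stoppers and (16×2 + 4×1)/20 = 1.80 for four, against 2.00 after deletion. The gaps are 5 and 10 points of the maximum.

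**The direction can reverse.** With two stoppers at 11 sessions and completers averaging 9, all starters average (18×9 + 2×11)/20 = 9.2, against 9.0 after deletion. Deletion then understates engagement.

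**Per-outcome reading.** The session count is present for everyone who started the condition, so nobody is deleted and the gap is zero.

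**The case against.** The strongest reply is that a complete-case analysis ordinarily drops only records that lack a value needed for the analysis in hand. A session count is not lacking, so the rule would delete nobody from engagement. The sentence also follows directly on the recall analyses, where it fits, and the protocol already says that sessions are counted for each participant. This reading is possible, but the SAP does not state it. Engagement is named earlier in the same paragraph and the closing sentence excludes nothing, so the ambiguity stands.

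Other parts of the reply limit the point:

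- A reader might infer that reported engagement was in fact overstated. The documents do not show this: they do not say that anyone withdrew or which reading was used. Section 6.0 is a general withdrawal and payment provision, not evidence of expected attrition.
- A reader might treat engagement as observed for every enrolled participant. It is known only for those who start a condition. Someone who leaves during the first week never starts the second condition, and the plan does not say whether that counts as zero or as not assessed.
- A reader might infer that acceptability is biased too. People who leave before the end of a week have no score for that week, but nothing in the documents gives a direction of error. Counts of missing scores are a reporting detail.
- Participants who skip many MEMI sessions but provide all the end-of-week data stay in on either reading, so much of the information on barriers to use is kept.

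**Conclusion.** The point holds as an ambiguity with a predictable consequence, not as a demonstrated error. Overstatement needs three things: a participant-level rule, at least one person who stops in the condition concerned, and stoppers who average fewer sessions than completers. The last is to be expected but is not guaranteed.

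Under the stated assumptions the MEMI overstatement is 6.7 points with two MEMI-week stoppers and 13.3 with four. The larger figure puts all four stoppers in the MEMI week, which is the least favourable split of four. The overstatement is zero on a per-outcome reading. It is also zero for MEMI if nobody stops in that week and Blocked-week stoppers with a MEMI count match completers. This is a cheap improvement: a better-defined primary summary from data already held.

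**What to change.** - Limit the complete-case rule to the paired recall t-tests, and define it there as both 1-week tests observed for the measure being compared.
- Report engagement by group and condition for every participant who started that condition. Count sessions not done, including those after withdrawal, as not completed. State the denominator and the number who never started.
- Summarise acceptability from all observed scores in each condition.

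The cost is a few sentences in the SAP and a recount of session data already collected. The downside is a possibly less favourable engagement figure. If nobody stopped early, or the rule was already applied per outcome, the engagement figures do not change and only the text becomes clearer.
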